8. SAFETY ANALYSIS

8.1. General

The safety analysis set will be used for all safety analyses. Summaries will be presented by treatment group and will represent what treatment was actually received, unless specified otherwise. Summaries of clinically significant abnormal values will include all postbaseline values (including scheduled, unscheduled, and IMPDV).

8.2. Duration of Exposure to IMP

Duration of exposure to IMP (days) for the individual patient is the number of days patient received drug (last day of IMP – first day of IMP + 1). Duration of treatment (days) will be summarized using descriptive statistics.

The last day of the IMP is determined by the study drug exposure date on patient’s electronic diary or the treatment completion/discontinuation date on the disposition page; whichever comes first. The reason is that in some cases, the question “*It is now time to take your study drug. Confirm that it was taken*” was continuing showing up on the AM3 device and it caused many confusions to patients who were on alternative medication, and should not need to answer this question after they were terminated from treatment.

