8.3. IMP Compliance

IMP compliance during the study will be assessed based on data collected with the dose counter device. This will be the primary method to evaluate the patient’s compliance rate. For patients who have a compliance rate of <80%, their handheld electronic diary will also be evaluated. A routine data monitoring report will be sent to a service provider to further investigate the issue (ie, diary data and IMP dose counter data are not consistent). Each of these individual patients will then be evaluated during the SDR meeting to determine whether the patient should be included in the PP analysis set.

The degree of IMP compliance will be determined by presenting the number of doses taken as a percentage of the number required by the protocol.

$$\text{Device: \% Compliance} = \frac{\text{Actual \# of actuations use per dose counter}}{\text{Expected \# of actuations to be used}} \times 100$$

$$\text{Diary: \% Compliance} = \frac{\text{Actual \# of actuations use per diary card}}{\text{Expected \# of actuations to be used}} \times 100$$

The denominator of “expected # of times study drug was to be taken” will be calculated based on patients’ participation in the study (ie, last day of IMP – first day of IMP + 1). For patients who complete the study treatment period, the last day of IMP used in the denominator calculation will

be the last expected dosing day. For early termination patients, the last day of IMP used in the denominator calculation will be the last expected dosing day before termination day. See Section 8.2 for last IMP date definition.

Patients are supposed to return their devices with dose counters at each visit. However, if there is no date for the return of the device in the database or a dose counter error has been reported, the treatment duration for that patient will be prorated according to the number and day when the device was returned without dose counter error. Table 10 below illustrates as an example for patient who has an unreturned device and reported dose counter error.

Table 10: Example of Unreturned Device or Dose Counter Error

Dispense Date	Return Date	Report Dose Counter Error	# of Days	# of Doses (total count)
02 April 2018	09 April 2018	--	7	12
09 April 2018	Device not returned	--	N/A	N/A
16 April 2018	30 April 2018	Reported on 20-April-2019	N/A	N/A
30 April 2018	14 May 2018	--	14	12
Overall compliance rate: $(12 + 12) / [(7 + 14+1)*2] = 57\%$				

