If a patient has missing electronic patient diary pages, it is assumed that this patient did not take the IMP on the days as expected.

Compliance with IMP will be categorized as <60%, 60% to <80%, 80% to <100%, and $\geq 100\%$ and summarized using descriptive statistics.

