8.4. Adverse Events

All adverse events will be coded using the MedDRA version 19.0. The incidence of adverse events will be summarized using descriptive statistics (counts and percentages) by SOC and preferred term (PT). Patients are counted only once in each SOC category, and only once in each PT category. Treatment-related adverse event summaries will include adverse events with missing relationship to study drug. For the summaries by severity, patients are counted at the greatest severity. Summaries will be presented for all treatment-emergent adverse events (overall and by severity), treatment-emergent adverse events determined by the investigator to be related to IMP (see FSS-AS-30003 protocol Section 7.1.4) (defined as related or with missing relationship, overall and by severity), serious treatment-emergent adverse events, treatment-emergent adverse events causing withdrawal from the study, and nonserious adverse events. Summaries will be presented by treatment group and for all patients.

Any event occurring after the patient has signed the study informed consent/assent form should be recorded and reported as adverse event. Those events occurring prior to the first dose of IMP will be considered as non-treatment-emergent adverse events, and those occurring on or after the first dose of IMP drug through 7 days after the last dose of IMP will be considered as treatment-emergent adverse events. Any events that occurred beyond the 7 days after the last dose of IMP will be considered as non-treatment-emergent adverse events.

For all non-treatment-emergent adverse events that occurred during the run-in period, a summary and a patient listing will be presented separately. All non-treatment-emergent adverse events that occurred 7 days after the last dose of IMP, prior to week 12 (mainly for patients who discontinued IMP but continued in the study) will be presented similarly. In addition, serious adverse events that were reported during the follow up period will be presented.

For all treatment-emergent adverse events that lead to discontinuation from IMP treatment through 7 days after the last dose of IMP will be summarized.

Patient listings of deaths, serious adverse events, adverse events leading to discontinuation, MedDRA dictionary terms for adverse event descriptions, and adverse event PT by patient number will be presented.

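### SAP 8.2 takes the earlier of the diary and disposition dates as the last IMP day, so a diary that ends for good before dosing ends understates exposure and, if the gap exceeds 7 days, closes the treatment-emergent window while the child is still on drug

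*SAP*

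**What the plan says.** SAP 8.2 computes exposure as last day of IMP minus first day plus one. The last day is the study drug date in the patient's "electronic diary or the treatment completion/discontinuation date on the disposition page; whichever comes first". The explanation is that the device went on asking for dose confirmation from children on alternative medication, who "should not need to answer this question after they were terminated from treatment".

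SAP 8.4 treats events from the first dose "through 7 days after the last dose of IMP will be considered as" treatment-emergent. It continues: "Any events that occurred beyond the 7 days after the last dose of IMP will be considered as non-treatment-emergent adverse events". A separate display covers "All non-treatment-emergent adverse events that occurred 7 days after the last dose of IMP, prior to week 12", described as mainly for children who stopped IMP but stayed in the study. The summary of treatment-emergent events leading to IMP discontinuation has the same 7-day limit.

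SAP 8.3 makes the dose counter the primary source for compliance, anticipates cases where "diary data and IMP dose counter data are not consistent", and refers back to 8.2 for the last IMP date. For missing diary pages "it is assumed that this patient did not take the IMP on the days as expected".

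Protocol Table 3 schedules observed dosing at RV/TV1 through TV6. Protocol 6.2.1 and 6.2.3 have the visit-morning dose recorded at the center.

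**The concern.** The stated problem is a diary date that is too late. Capping the diary at the disposition date solves it. Taking whichever date is earlier also accepts a diary date that is too early, and the SAP gives no reason for that. Neither the dose counter nor a site-observed dose can correct it.

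The last IMP date drives the exposure summary. Because 8.2 holds the SAP's only definition, it presumably also drives the treatment-emergent window. A child who stops logging, keeps dosing and then has an event more than 7 days after the last log would be counted as off drug. If that event led to stopping IMP, it would also drop out of the treatment-emergent discontinuation summary. On-drug events would then sit in a display meant mainly for children off drug.

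**Working it through.** The plan states no figure to reproduce, so the check applies its rules directly.

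**Inputs from the documents.** SAP 8.2: last IMP day = min(diary date, disposition date); exposure = last day − first day + 1. SAP 8.4: window closes at last dose + 7. Protocol Table 3: visits on nominal days 1, 8, 15, 29, 57 and 85.

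**Assumptions, not in the documents.** First dose day 1; true last dose and disposition date both day 85; last logged dose on day L, with no later diary entry.

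**Formulas.** Exposure lost = 85 − L. Window closes on L + 7 instead of 85 + 7 = 92. On-drug days outside the window = max(0, 85 − L − 7).

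| L | Exposure under 8.2 | Days lost (of 85) | Window closes | On-drug days outside |
|---|---|---|---|---|
| 80 | 80 | 5 (6%) | 87 | 0 |
| 78 | 78 | 7 (8%) | 85 | 0 |
| 77 | 77 | 8 (9%) | 84 | 1 |
| 71 | 71 | 14 (16%) | 78 | 7 |
| 57 | 57 | 28 (33%) | 64 | 21 |
| 43 | 43 | 42 (49%) | 50 | 35 |

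Any final gap costs exposure. Reclassification of on-drug events starts only when the gap passes 7 days.

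**The case the SAP had in mind.** IMP stopped on day 40, prompts answered to day 85: min(85, 40) = 40, which is right. A cap gives the same answer, so the extra reach of the rule is not needed for it.

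**If visit-morning doses do enter the diary.** A completer dosed at TV6 then has a diary date of day 85 and loses nothing. The remaining risk is a child who stops logging after a visit and discontinues before the next one. At nominal visit days, and discontinuing at the latest on the day before the next visit:

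- After TV1 or TV2 (7-day interval): gap at most 6 days, none outside the window.
- After TV3 (days 15 to 29): gap at most 28 − 15 = 13, at most 13 − 7 = 6 on-drug days outside.
- After TV4 or TV5 (28-day interval): gap at most 56 − 29 = 84 − 57 = 27, at most 27 − 7 = 20 on-drug days outside.

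The day 57 and day 43 rows of the table therefore require at least one visit dose that never reached the diary.

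**The case against.** The strongest reply is that trial procedures largely prevent the problem. Visit-morning doses are recorded at the center, and staff must check at each visit that the diary is up to date, look for missing data and download the device (Protocol Table 3, footnote k). The documents do not say outright that the visit dose is entered in the handheld, but if it is, most completers are protected. This stands, and it narrows the point mainly to children who discontinue between visits or whose visit dose was not captured.

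Next, reclassified events remain visible. Those before week 12 get their own summary and listing, and the SAP 8.4 listings of deaths, serious events and events leading to discontinuation carry no stated treatment-emergent restriction. A reader might infer that events disappear from the report; the documents do not support that. The treatment-emergent tables are what change.

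Third, 8.4 never cites 8.2. The link is an inference from 8.2 being the only definition. It is a reasonable one, but the SAP should make it explicit.

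Fourth, counting missing diary pages as not dosed in 8.3 is an existing convention that 8.2 follows. A reader might infer that the SAP declares the diary the less reliable source; 8.3 ranks the counter first only for the compliance rate. Even so, the 8.3 diary review is tied to counter compliance below 80%, so it would not reliably catch a child who doses well but has stopped logging.

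**Conclusion.** The point holds as a mismatch between a rule and its reason, with a limited consequence. A diary that ends for good before dosing ends shortens recorded exposure by the whole gap. It puts on-drug days outside the treatment-emergent window only beyond the seventh day of the gap.

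The frequency is unknown. The documents give no rate of early diary cessation, so no trial-level percentage can be stated, and the visit procedures suggest that the effect is probably small.

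Two stronger readings are tempting. One is that any diary lapse, or a replaced handheld, costs exposure; it does not, because a later entry restores the date. The other is that the comparison between arms is biased; nothing in the documents shows that logging lapses differ by arm.

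The conclusion assumes that the last dose in 8.4 means the date defined in 8.2.

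**What to change.** In SAP 8.2, define the last IMP date as the latest documented dose, meaning the last diary-confirmed dose or the last site-observed or visit-recorded dose, capped at the treatment completion/discontinuation date on the disposition page. Cite that date in 8.4. Logging to day 57 with an observed dose on day 85 then gives min(max(57, 85), 85) = 85, and the window closes on day 92. The child stopped on day 40 who answers prompts to day 85 still gets day 40. A child with no documented dose after the last log keeps the diary date, so exposure is not stretched to the disposition date by default.

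This does not reach a child who stops logging after a visit and discontinues before the next, since no site-observed dose falls in between. For those children, where the returned dose counter shows clearly more doses than the diary up to its last entry, settle the date at the blinded Statistical Data Review meeting. Do not derive a date from the counter: it gives a count and a return date, not dose dates.

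Before finalizing, confirm whether visit-morning doses enter the handheld and whether observed doses are held as dated records; the documents show neither.

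The cost is a small derivation change before database lock, some case review, and a few more events counted as treatment-emergent.

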8.3. IMP Compliance

IMP compliance during the study will be assessed based on data collected with the dose counter device. This will be the primary method to evaluate the patient’s compliance rate. For patients who have a compliance rate of <80%, their handheld electronic diary will also be evaluated. A routine data monitoring report will be sent to a service provider to further investigate the issue (ie, diary data and IMP dose counter data are not consistent). Each of these individual patients will then be evaluated during the SDR meeting to determine whether the patient should be included in the PP analysis set.

The degree of IMP compliance will be determined by presenting the number of doses taken as a percentage of the number required by the protocol.

$$\text{Device: \% Compliance} = \frac{\text{Actual \# of actuations use per dose counter}}{\text{Expected \# of actuations to be used}} \times 100$$

$$\text{Diary: \% Compliance} = \frac{\text{Actual \# of actuations use per diary card}}{\text{Expected \# of actuations to be used}} \times 100$$

The denominator of “expected # of times study drug was to be taken” will be calculated based on patients’ participation in the study (ie, last day of IMP – first day of IMP + 1). For patients who complete the study treatment period, the last day of IMP used in the denominator calculation will

be the last expected dosing day. For early termination patients, the last day of IMP used in the denominator calculation will be the last expected dosing day before termination day. See Section 8.2 for last IMP date definition.

Patients are supposed to return their devices with dose counters at each visit. However, if there is no date for the return of the device in the database or a dose counter error has been reported, the treatment duration for that patient will be prorated according to the number and day when the device was returned without dose counter error. Table 10 below illustrates as an example for patient who has an unreturned device and reported dose counter error.

Table 10: Example of Unreturned Device or Dose Counter Error

Dispense Date	Return Date	Report Dose Counter Error	# of Days	# of Doses (total count)
02 April 2018	09 April 2018	--	7	12
09 April 2018	Device not returned	--	N/A	N/A
16 April 2018	30 April 2018	Reported on 20-April-2019	N/A	N/A
30 April 2018	14 May 2018	--	14	12
Overall compliance rate: $(12 + 12) / [(7 + 14+1)*2] = 57\%$				

If a patient has missing electronic patient diary pages, it is assumed that this patient did not take the IMP on the days as expected.

Compliance with IMP will be categorized as <60%, 60% to <80%, 80% to <100%, and $\geq 100\%$ and summarized using descriptive statistics.

8.4. Adverse Events

All adverse events will be coded using the MedDRA version 19.0. The incidence of adverse events will be summarized using descriptive statistics (counts and percentages) by SOC and preferred term (PT). Patients are counted only once in each SOC category, and only once in each PT category. Treatment-related adverse event summaries will include adverse events with missing relationship to study drug. For the summaries by severity, patients are counted at the greatest severity. Summaries will be presented for all treatment-emergent adverse events (overall and by severity), treatment-emergent adverse events determined by the investigator to be related to IMP (see FSS-AS-30003 protocol Section 7.1.4) (defined as related or with missing relationship, overall and by severity), serious treatment-emergent adverse events, treatment-emergent adverse events causing withdrawal from the study, and nonserious adverse events. Summaries will be presented by treatment group and for all patients.

Any event occurring after the patient has signed the study informed consent/assent form should be recorded and reported as adverse event. Those events occurring prior to the first dose of IMP will be considered as non-treatment-emergent adverse events, and those occurring on or after the first dose of IMP drug through 7 days after the last dose of IMP will be considered as treatment-emergent adverse events. Any events that occurred beyond the 7 days after the last dose of IMP will be considered as non-treatment-emergent adverse events.

For all non-treatment-emergent adverse events that occurred during the run-in period, a summary and a patient listing will be presented separately. All non-treatment-emergent adverse events that occurred 7 days after the last dose of IMP, prior to week 12 (mainly for patients who discontinued IMP but continued in the study) will be presented similarly. In addition, serious adverse events that were reported during the follow up period will be presented.

For all treatment-emergent adverse events that lead to discontinuation from IMP treatment through 7 days after the last dose of IMP will be summarized.

Patient listings of deaths, serious adverse events, adverse events leading to discontinuation, MedDRA dictionary terms for adverse event descriptions, and adverse event PT by patient number will be presented.

8.5. Deaths

If any patient dies during the study, all relevant information will be discussed in the patient's narrative included in the CSR.

8.6. Asthma Exacerbations

Asthma exacerbations that requires a change in medication or worsening of asthma that requires the patient to be treated with alternative therapy will be entered into the case report form (CRF), including the date at which any medication change was made and whether this medication change was implemented prior to or after the IMPDV lung function assessments (FEV₁ and PEF) were completed. Asthma worsening including asthma exacerbations with a change to alternative asthma therapy will not be considered an adverse event for this study since it is an expected outcome for this study in an asthmatic patient population. Asthma exacerbations that meet the criteria for a serious adverse event will be recorded as adverse events. For the purpose of this study, an asthma exacerbation is defined as worsening of asthma requiring any significant treatment other than IMP and study rescue medication.

The number and percentage (%) of patients experiencing an asthma exacerbation will be presented by treatment group.

A summary of the number and percentage of patients with asthma exacerbations resulting in hospitalization, leading to permanent withdrawal of study drug, and other actions will be presented by treatment group.

The number and percentage of patients with asthma exacerbations will be presented by maximum severity and treatment group. Severity will be classified as "mild", "moderate", or "severe". If a patient experiences more than 1 asthma exacerbations, only the asthma exacerbations with the greatest severity will be included in the summary table.

In all of the above summaries, each patient will be counted only once regardless of the number of asthma exacerbations experienced during the study.

8.7. Clinical Laboratory Tests

Clinical laboratory tests of chemistry, hematology, and urinalysis parameters are not collected for this study. However, optional clinical laboratory evaluation at the discretion of the investigator will be listed. All clinical laboratory tests will be listed (if any) to ensure the safety of the patients.

8.8. Physical Examinations

Physical examinations, including height (to be measured at the screening visit only) and weight, will be performed at the SV, RV and at the final treatment visit (TV6 or at the IMPDV). Patients with a physical examination, patients with at least 1 abnormal finding, and abnormal findings for each category will be summarized at baseline using descriptive statistics. Any physical examination finding that is judged by the investigator as a clinically significant change (worsening) compared with a baseline value will be considered an adverse event, recorded on the CRF, and monitored as described in Section 7.1.2 of the FSS-AS-30003 study protocol.

Shifts (normal and abnormal) from baseline to final treatment visit will be summarized by treatment for each physical examination category.

Descriptive statistics for weight and height will be provided and a listing of physical examinations by patient and all abnormal findings will be provided.

8.9. Vital Signs

Summary statistics for vital signs (blood pressure and pulse) will be presented at each visit throughout the study. Vital signs values and changes from baseline to each visit will be summarized using descriptive statistics. Height and weight will be recorded at SV and TV6/IMPDV.

[Table 11](#) specifies the criteria for identifying vital signs as potentially clinically significant abnormal values. Note that in order to be identified as potentially clinically significant abnormal, a value needs to meet both criteria below: ie, have a value beyond the criterion value and a change of at least the magnitude specified in the change relative to baseline column. The potentially clinically significant abnormal vital signs values will include all post baseline values (including scheduled, unscheduled, and early termination visits) for the summaries.

Table 11: Criteria for Potentially Clinically Significant Vital Signs

Age (years)	Criterion Value			Change relative to baseline		
	4-5	6-8	9-11	4-5	6-8	9-11
Pulse (bpm)	>135	>130	>110	Increase of ≥ 25	Increase of ≥ 20	Increase of ≥ 20
	<65	<60	<60	Decrease of ≥ 25	Decrease of ≥ 20	Decrease of ≥ 20
SBP (mmHg)	>110	>120	>130	Increase of ≥ 20	Increase of ≥ 20	Increase of ≥ 20
	<80	<80	<80	Decrease of ≥ 20	Decrease of ≥ 20	Decrease of ≥ 20
DBP (mmHg)	>80	>80	>80	Increase of ≥ 15	Increase of ≥ 15	Increase of ≥ 15
	<50	<50	<50	Decrease of ≥ 15	Decrease of ≥ 15	Decrease of ≥ 15

Abbreviations: bpm=beats per minute; DBP=diastolic blood pressure; mmHg=mm of mercury; SBP=systolic blood pressure.

Note: All ranges are adapted from The Harriet Lane Handbook of Pediatrics, 20th ed, 2015. Pulse: Table 7-4. Blood pressure: Table 7-1.

